Different risk assessment tools have been proposed for patients undergoing AHA(11)(12). The APACHE-II score, even though developed for critical care, seems to be the one with best prediction of outcome. Risk assessment tools are important to support clinical decision making by the perioperative team as subjective clinical assessment often underestimates the risk for the patients in highest risk of complications and death(13). Good clinical decision-making is likely to improve the clinical outcome by allocating appropriate resources. Prognostic tools are also useful to inform patients about what to expect in the immediate postoperative phase and of long-term outcome. Especially in the elder population with increased risk of long hospitalisation and loss of function or independency this can be useful to give informed consent to treatment strategy. Furthermore, good risk assessment is

important to optimize palliative care after end-of-life decisions, which is often ignored in research, but highly relevant in clinical work.

During recent years use of prognostic biomarkers in other high mortality populations have received much attention for risk stratification(14). An ideal biomarker should be readily available upon decision-making, easy to measure, reliable and biologically stable. Furthermore it has to be able to accurately differentiate prognosis for patients to have value in the clinical decision-making and guide the treatment of the patient. It should be linked to the clinical outcomes.

We aim to identify serological AHA biomarkers that are prognostic or predictive for postoperative morbidity, mortality and length of hospitalisation.

Potential biomarkers:

Inflammation markers:

Soluble urokinase-type plasminogen activator receptor (SUPAR) is a relatively new potential biomarker for inflammation. It is related to mortality in critically ill patients(15) especially in combination with the APACHE II score(16)(17). SUPAR is thought to be related to the inflammation reaction and endothelial dysfunction affected in critically ill patients(18). It is furthermore related to cardiovascular disease and subclinical organ damage(19) and is shown to be relatively stable throughout the day without circadian variations. It is related to all-cause mortality in major cohorts from different parts of the world(20). It has been suggested that the biomarker can be used to strengthen risk stratification for patients presenting acutely at the emergency department(21).

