We will establish a new research bio bank based on material from the samples collected in relation to the standard treatment according to the AHA-protocol (one EDTA-tube and one tube with coagulation enhancer). The research biobank will be reported to the Danish Data Protection Agency. After approval the biological material will be kept in the research biobank until the end of the study, at which time the samples have been used entirely or will be transferred back to the biobank from which they originally were taken. The present study is expected finalized by May 1, 2022.

Analysis of the samples from the biobank will require approval by the Ethics Committee including dispensation from obtaining consent from involved patients. Retrospective consent is impossible to obtain as a large proportion of patients have died since the data collection started, and analysis of the data set without the patients, who have died is worthless as a predictive tool. Research on this vulnerable population with high mortality and morbidity is very limited. It is therefore an important ethical aspect that the collected data can be used for research, which may be beneficial for future critically ill, emergency patients.

Approval for these studies will be applied from the Ethics Committee of the Capital Region of Denmark. Referral of data from the AHA quality improvement project to this study will be registered and approved by the Danish Data Protection Agency. The biological material and non-anonymous data, from both the research bio bank and the samples collected in relation to standard treatment, will be destroyed when the approval from the Danish Data Protection Agency expires.

We will search the national register for usage of biological tissue, “Vævsanvendelsesregistret”, for patients who only wish their tissue is used for their own treatment. Samples from these patients will not be included in this project.

Risks, side effects and harms

Potential harms for the participants are limited as the research is focused on preoperative risk assessment and not long-term prediction of future diseases. There is therefore a low risk of findings that may affect the participants. The biomarkers we wish to study have in similar studies of critically ill patients not shown any random findings affecting the participants.

Population

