We will include patients with a preoperative blood sample stored in the bio bank; the patients did undergo AHA at Hvidovre Hospital, Copenhagen, Denmark, from June 1st 2013 when the AHA study protocol was initiated.

Inclusion criteria were: Patients aged 18 or older with the suspicion for abdominal pathology requiring immediate emergency laparotomy or laparoscopy including reoperations after elective surgery and reoperations after previous AHA surgery.

We excluded the following procedures: appendectomies; negative laparoscopies and laparotomies; cholecystectomies; simple herniotomies following incarceration (without intestinal resection); reoperation due to fascial separation with no other abdominal pathology; internal herniation after roux-en-y gastric bypass surgery; sub-acute surgery (planned within 48 hours) for inflammatory bowel disease; and sub-acute colorectal cancer surgery.

We excluded, traumas, pregnant woman, uro-genital, gynaecological and vascular pathology except for mesenteric ischemia.

Data collection

Data on mortality was obtained using the Danish Civil Registration System(30). This register is maintained by the Danish government and assigns a unique personal identification number to all Danish citizens. It contains data on address, immigration emigration, gender, date of birth and exact day of death. It is updated within days of any change in information.

Other data were collected in the medical records of patients. Complications were defined using the Clavien-Dindo Classification for Surgical Complications(31).

Outcome measures

Primary outcomes are short and long-term mortality (30 days and 180 days respectively) and major complications during index hospitalization (Clavien-Dindo >2). Secondary outcomes are length of hospitalisation, length of intensive care admission as well as perioperative need for inotropic or vasopressor support and high volume fluid resuscitation.

Description of biological material

Blood samples were collected at the time of induction of anaesthesia. For AHA-patients a pre-operative optimisation protocol was introduced in the hospital throughout the data collection period, which stated that the patient was optimized with goal directed fluid therapy before induction of anaesthesia. The blood samples were usually taken from the arterial line used for invasive blood pressure monitoring but some were obtained from venous puncture with standard preoperative tests.

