The blood samples were collected in tubes with EDTA as anti-coagulant for plasma and in tubes with coagulation enhancer for serum. After centrifugation for 10 mins at room temperature the plasma and serum, respectively were transferred to freezing tubes for subsequent long-term storage at -80C.

Biochemical analysis

A predefined biochemical analysis protocol for each biomarker will be followed. The methods used will be described in the specific published studies.

Statistical analysis protocol

Data will be analysed using the SPSS, STATA, R or SAS software. Tests will be two-sided with $p<0.05$ considered to be significant.

Missing data will be assessed using Little's test for data missing completely at random(32). If data is not missing completely at random multiple imputation will be performed(33).

All patients or random samples (with a size defined by a preoperative sample size estimation) from the AHA cohort with blood samples taken preoperatively will be included in the analysis. Baseline characteristics will be presented and for biomarkers with continuous data patients will be stratified into quartiles or tertiles. Characteristics of populations will be presented as frequencies for categorical variables and medians with inter-quartile range for continuous variables. Differences between groups will be presented using appropriate statistical tests. Kaplan-Meier curves will be produced for the primary outcomes and compared using the log-rank test. COX-regression will be used to perform multivariate analyses adjusted for potential confounders with Bonferroni correction.

Receiver operating characteristic curves for each biomarker will be produced for the primary outcomes. Area under the curve will be measured to evaluate the prognostic value of the biomarkers.

Limitations of the study

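### Kaplan-Meier and log-rank are planned for in-hospital major complications, which are observed only until discharge, with no fixed day and no rule for patients discharged alive

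*Combined protocol and SAP*

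**What the plan says.** The protocol's Outcome measures section names three primary outcomes: death by 30 days, death by 180 days, and "major complications during index hospitalization (Clavien-Dindo >2"). Length of hospitalisation is a secondary outcome.

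Under Statistical analysis protocol, biomarkers with continuous values are grouped ("patients will be stratified into quartiles or tertiles"), and then "Kaplan-Meier curves will be produced for the primary outcomes and compared using the log-rank test". No primary outcome is excepted. Cox regression follows for adjusted analyses, without saying for which outcomes. The same section adds "Receiver operating characteristic curves for each biomarker will be produced for the primary outcomes".

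On data sources, the Data collection section takes deaths from the civil register: "It contains data on address, immigration emigration, gender, date of birth and exact day of death". For everything else it says only "Other data were collected in the medical records of patients".

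**The concern.** Kaplan-Meier and log-rank need an event date, a time origin, and a rule for patients who leave observation without the event. The two mortality outcomes have what they need: a horizon in days, and a register that follows patients beyond discharge. The complication outcome does not. Its window is each patient's own stay, and a patient who goes home can no longer have the event. The plan does not say whether such a patient is censored at discharge or kept event-free to some day. Nor does it say that complication dates exist.

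The choice matters because the two rules answer different questions. Censoring at discharge treats patients who went home as if they remained at risk of an in-hospital event. Keeping them event-free gives something close to a comparison of proportions. The stated aim is: "We aim to identify serological AHA biomarkers that are prognostic or predictive for postoperative morbidity, mortality and length of hospitalisation". A biomarker that meets it could separate strata both by complications and by length of stay, and that is the setting in which the two rules can diverge. Two analysts following the text could report different curves and p-values for a primary outcome.

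**Working it through.** **No figure to reproduce.** The documents state no event rate, sample size or power. Every rate and group size below is assumed, and serves only to show when the missing rule matters.

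**The texts side by side.**

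| | Mortality | In-hospital major complications |
|---|---|---|
| Horizon | 30 and 180 days | the patient's own stay |
| Event date | exact day, register | medical records, dating not stated |
| After discharge | still observed | cannot occur |
| Rule for discharge alive | not needed | none given |

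**Model.** Complication hazard a·exp(−t/τ) per day, with cumulative hazard Hc(t) = a·τ·(1 − exp(−t/τ)). Discharge hazard d per day from day 3, with cumulative hazard Hd(t). Horizon 30 days.

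- True in-hospital risk = ∫ a·exp(−t/τ)·exp(−Hc(t) − Hd(t)) dt over 0 to 30.
- 1 minus Kaplan-Meier with discharge censored tends to 1 − exp(−Hc(30)).

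**Step 1, the curve.** Take a = 0.06, τ = 6, d = 0.10.

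- Hc(30) = 0.06 × 6 × (1 − e^−5) = 0.358, so the Kaplan-Meier figure is 1 − e^−0.358 = 30.1%.
- The integral gives a true risk of 24.1%, so the curve is 6 points too high.
- If nearly all complications precede the first discharge (a = 0.6, τ = 0.5), both are 25.9%.

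**Step 2, the test.** Higher-risk group: a = 0.09, d = 0.08 (true risk 34.9%, Kaplan-Meier 41.5%). Lower-risk group: a = 0.06, d = 0.12 (23.4%, 30.1%). τ = 6 throughout. Simulated power at two-sided 5%, 20,000 runs (Monte Carlo standard error at most 0.35 points):

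| Design | Log-rank, discharge censored | Log-rank, discharged kept event-free to day 30 | Chi-square on yes/no |
|---|---|---|---|
| 2 groups of 150 | 46% | 58% | 59% |
| 2 groups of 300 | 76% | 87% | 87% |
| 3 tertiles of 100, middle group a = 0.075, d = 0.10 | 25% | 33% | 34% |
| 2 groups of 150, equal discharge rate 0.10 | 47% | 46% | 46% |

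**Step 3, dependence on timing.** Hold a·τ at 0.54 and 0.36 (ratio 1.5), keep the step 2 discharge rates and 150 per group, and vary only τ. The rows for 4 days and below use 4,000 runs, standard error at most √(0.25/4000) = 0.8 points:

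| Decay constant τ | Log-rank, discharge censored | Chi-square |
|---|---|---|
| 6 days | 46% | 59% |
| 4 days | about 50% | 58% |
| 3 days | 53% | 58% |
| 2 days | 54% | 56% |
| 1 day | 56% | 55% |

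The loss is 13 points at 6 days, about 8 at 4 days, and nil within simulation error at 1 day. Moving the first discharge to day 5, with τ = 6, gives about 51% against 58%.

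**Step 4, same complication hazard, different discharge rates.** With a = 0.06 in both groups, τ = 6 and discharge at 0.08 against 0.12, rejection is 5% by discharge-censored log-rank and 6% by chi-square, so a mild contrast makes little difference.

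**The case against.** **The plan may already allow the right analysis.** Just before the Kaplan-Meier sentence, it promises suitable tests for differences between groups. That line follows the text on baseline characteristics, so its reach to outcomes is uncertain, and it does not remove complications from the sentence that follows. The area under the ROC curve, which the plan names as its measure of prognostic value, survives intact. This narrows the point without removing it.

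**The index stay is an observation window.** It is. What is missing is a fixed day, or a rule for the end of the stay.

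**Discharge-censored log-rank is a valid test.** It is valid for the daily hazard among patients still admitted. A reader might infer that the planned test is invalid or has a wrong type I error; that does not follow. It is aimed at a different quantity from the in-hospital outcome as defined.

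**The power loss rests on chosen assumptions.** This stands. It needs discharge-censoring, which the plan does not state, together with slower discharge in the higher-risk stratum and complications spread over the stay. A harsher example is easy to build. With a constant complication hazard of 0.03 per day in both groups, discharge at 0.10 against 0.05 and 250 per group, true risks are 0.03/0.13 = 23% and 0.03/0.08 = 37.5%. Rejection is then 4% by discharge-censored log-rank and 94% for the yes/no comparison. A reader might infer that the plan will miss real differences. Nothing in the documents supports a constant hazard or a twofold discharge contrast.

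**In-hospital death may already be an event.** A reader might infer that the plan mishandles death in this analysis. The threshold has no upper limit, so death may be counted already. The text does not settle it, and only a clarification is warranted.

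**Conclusion.** The point holds in a narrow form. For one of three primary outcomes the plan names a time-to-event method without the end-of-stay rule it needs, and without saying that the necessary dates exist. That much is read directly from the text and rests on no assumed rate.

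The consequences are conditional. If discharge is censored and complications continue after the first discharges, the curve overstates in-hospital risk (by 6 points in the assumed example). Power may fall by up to 13 points in the two-group examples of steps 2 and 3, or hardly at all. If discharged patients are kept event-free, power is within about a point of the chi-square test. The documents cannot show which case applies, so no claim that the analysis will be biased or underpowered is supported. The 30-day and 180-day mortality analyses and the ROC analysis are not affected. This is a cheap improvement.

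**What to change.** Replace the Kaplan-Meier sentence under Statistical analysis protocol, and limit the Cox sentence, along these lines:

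> *Kaplan-Meier curves, log-rank tests and Cox regression will be used for 30-day and 180-day mortality. In-hospital major complications (Clavien-Dindo >2) will be analysed as a yes/no outcome: proportions compared across biomarker strata, logistic regression for adjusted analysis, and ROC curves as planned.*

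If timing is wanted and complication dates exist, use cumulative incidence with discharge alive as a competing event, and state the horizon.

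As a side clarification, state whether in-hospital death is included in Clavien-Dindo >2.

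The cost is two or three sentences and no new data. The downside is that the yes/no analysis gives up timing information. The optional timing analysis depends on dates that the documents do not say were recorded.

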IL-10, IL-6, Tumor Necrosis Factor alpha, IP-10 are other markers of inflammation that regulate the inflammatory response to disease. It is proposed that increased synthesis or reduced metabolism of IL-6 is related to poor outcome in sepsis(22).

Troponin:

Troponin is a well-established biomarker for myocardial infarction. Recent studies show that it is related to the APACHE II score and could be useful as a biomarker for overall mortality in critically ill patients with severe sepsis(23)(24)(25).

Endothelial dysfunction

Markers of endothelial function have been suggested to predict poor outcome. Syndecan-1, a transmembrane endothelial proteoglycan, which in serum is a marker of glycocalyx degradation, is related to mortality in trauma patients(27).

Endocrine and other markers

The endocrine system is highly involved in the surgical stress response and imbalances in hormonal response to stress could potentially predict outcome. Especially catecholamines are involved in the inflammatory response and related to endothelial dysfunction(27).

Furthermore, combination of different molecular biomarkers could be of interest to create the best possible molecular risk assessment tool(14).

Methods

Manuscripts will be prepared using the STROBE-ME statement guidelines(29).

Approvals and ethical considerations:

Danish legislation “Lov om behandling af personoplysninger” will be followed and the study will be reported to the Danish Data Protection Agency.

Data used in these studies are collected in the quality improvement program “Acute High-Risk Abdominal Surgery study – an optimized Perioperative Course (AHA)” (ClinicalTrials.gov Identifier: NCT01899885) approved by the Danish Data Protection Agency (jr.no. 2007-58-0015) **HVH-2013-052** in 2013. In this program patients were enrolled in a standardized protocol of perioperative optimization. The standardized protocol included collection of blood samples for future research.

Patients were informed about the AHA protocol and gave informed consent where possible. If patients were in a state where informed consent was not possible informed consent was sought from relatives.

As this was a qualitative improvement programme, it did not require approval by an ethical committee according to Danish law. Blood samples were drawn and collected with the standard preoperative tests and stored at -80C in a biobank.

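### For test decisions within one family of Cox tests, Holm's step-down procedure is never less powerful than the planned Bonferroni correction at the same familywise error: an optional gain, not an error

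*Combined protocol and SAP*

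**What the plan says.** The Statistical analysis protocol sets the general level: "Tests will be two-sided with $p<0.05$ considered to be significant". For the adjusted survival models it adds: "COX-regression will be used to perform multivariate analyses adjusted for potential confounders with Bonferroni correction". No step-down variant is named, so the ordinary single-step reading applies, with each test judged at 0.05/m. The section does not give m. It also does not say whether the family runs over biomarkers, outcomes, tertile or quartile contrasts, or separate papers. The correction is attached to the Cox models only.

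Two other places bear on the size of the family. Outcome measures lists three primary outcomes: "Primary outcomes are short and long-term mortality (30 days and 180 days respectively) and major complications during index hospitalization (Clavien-Dindo >2". The background on potential biomarkers names seven markers individually: SUPAR, four cytokines ("IL-10, IL-6, Tumor Necrosis Factor alpha, IP-10 are other markers of inflammation that regulate the inflammatory response to disease"), troponin and syndecan-1. It also mentions catecholamines, as a class of unstated number. Biochemical analysis and Publication of results both foresee more than one published study.

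**The concern.** Single-step Bonferroni holds every test to the same strict threshold, however many of the others have already been rejected. Holm relaxes the threshold after each rejection without giving up familywise control and without any assumption on how the tests are correlated. If several markers really are associated with outcome, some that Holm would declare significant would be missed under the planned rule, although the error guarantee is the same. At stake is some power for the second and later associations. The validity of the analysis is not in question.

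**Working it through.** **Inputs.** From the documents: two-sided 0.05; three primary outcomes; seven named markers plus catecholamines. Assumed, because the documents are silent:
- catecholamines count as one marker, giving 8 markers and 8 × 3 = 24 tests;
- alternatively, one marker per paper, giving m = 3;
- mean z of 3.0 for each true association, and exchangeable correlation 0.5 between tests.

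The plan states no figure of its own to reproduce.

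**1. The planned method is valid.** With independent true nulls, the familywise error at 0.05/m is 1 − (1 − 0.05/m)^m: 0.0492 for m = 3 and 0.0488 for m = 24. Uncorrected it would be 1 − 0.95^3 = 0.143 and 1 − 0.95^24 = 0.708, so some correction is warranted.

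**2. Holm's thresholds.** Order the p-values. Compare the smallest with 0.05/m, the next with 0.05/(m − 1), and so on to 0.05, stopping at the first failure.
- m = 3: 0.0167, 0.025, 0.05, against a constant 0.0167.
- m = 24: 0.00208, 0.00217, 0.00227, …, 0.05, against a constant 0.00208.

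The first threshold equals Bonferroni's and every later one is larger. Holm therefore rejects whatever Bonferroni rejects. No simulated data set broke this rule.

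**3. Bonferroni power per true association, directly.** Power ≈ Φ(3.0 − c), where c is the two-sided critical value at 0.05/m.
- m = 24: c = 3.078, Φ(−0.078) = 46.9%.
- m = 3: c = 2.394, Φ(0.606) = 72.8%.

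**4. Holm's gain, by simulation** (40,000 or more sets per scenario; repeat runs agree to about 0.2 points). The Holm column is Bonferroni plus gain.

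| m | True effects | Bonferroni | Gain (points) | Holm |
|---|---|---|---|---|
| 24 | 1 | 46.9% | 0.0 | 46.9% |
| 24 | 3 | 46.9% | 0.5 | 47.4% |
| 24 | 6 | 46.9% | 1.3 | 48.2% |
| 24 | 12 | 46.9% | 3.3 | 50.2% |
| 24 | 18 | 46.9% | 6.1 | 53.0% |
| 24 | 24 | 46.9% | 11.4 | 58.3% |
| 3 | 1 | 72.8% | 0.1 | 72.9% |
| 3 | 2 | 72.8% | 3.1 | 75.9% |
| 3 | 3 | 72.8% | 7.3 | 80.1% |

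**5. Error control and first discovery.** At correlation 0.5, Holm's familywise error never exceeded 0.042 in these scenarios. It was about 0.034 to 0.036 for m = 24 with few true effects, and about 0.041 for m = 3 with one. The chance of at least one true discovery is essentially the same under both methods, for example 90.8% against 90.8% for m = 24 with 12 true effects. This is because the first Holm step is the Bonferroni threshold.

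**6. Sensitivity.** With independent tests and a weaker effect (80% power at unadjusted 0.05), the pattern for m = 8 is the same: 53.0% against 53.1% with 1 real effect, 52.7% against 55.9% with 4, and 52.6% against 64.2% with all 8.

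**The case against.** The strongest reply is that nothing in the plan is wrong. Bonferroni is valid and conservative, and choosing it is a legitimate preference. That stands.

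A reader might go further and infer that the switch is free. It is not, for two reasons.
- **Intervals.** Bonferroni has simple matching simultaneous intervals for the hazard ratios, at level 1 − 0.05/m. Holm has none as simple. As an illustration, take m = 3 and p-values 0.010, 0.020 and 0.030. Holm rejects all three (0.010 ≤ 0.0167, 0.020 ≤ 0.025, 0.030 ≤ 0.05). The 98.33% intervals for the last two would still include a hazard ratio of 1. The plan does not promise simultaneous intervals, which limits this objection but does not remove it.
- **Several papers.** Holm needs all p-values of a family together. A pre-fixed 0.05/m can be applied paper by paper, whereas Holm across papers cannot be finished until the last one. The plan does not say that a family across papers is intended. If each paper is its own family, Holm works within it, but a 24-test family then need not exist and the m = 3 rows may be nearer the truth.

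A reader might also take the 11-point figure as the expected gain, on the view that most of the markers should be related to mortality. The documents do not support that. They call the markers potential ones. The mortality links they state are for SUPAR and troponin, mainly in critically ill or septic patients, and for syndecan-1 in trauma. IL-6 is tied to poor outcome in sepsis, and no mortality link is stated for IL-10, TNF-alpha or IP-10. The 11.4 points require every marker to be truly associated with every outcome after adjustment.

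Finally, Holm needs the same m that Bonferroni needs, and the plan does not fix it. Between m = 3 and m = 72 (24 tests × 3 quartile contrasts), 0.05/m runs from 0.0167 to 0.0007. That gap matters more than the choice between the two methods, and changing the method alone would not close it.

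**Conclusion.** The point holds as an optional improvement of low priority. For test decisions within one jointly analysed family, Bonferroni is never more powerful than Holm at the same familywise error, whatever m is and however the tests are correlated. That part rests on no assumption about this study.

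The size of the gain does rest on assumptions. With mean z 3.0 and correlation 0.5 it is about 0 to 11 points of average power for m = 24 and about 0 to 7 points for m = 3. It is near zero when true effects are few, and there is practically no change in the chance of finding at least one. The documents give no number of tests, effect size or event count that would narrow this range. A reading that Bonferroni is an error, or that it invalidates the Cox results, is not supported.

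**What to change.** In the Statistical analysis protocol, replace Bonferroni correction with: *Holm step-down correction at familywise 0.05, applied within each publication's pre-stated family of Cox tests and reported as adjusted p-values.* State in the same place which markers, outcomes and contrasts form each family, before the results are seen. The adjusted p-value for the i-th smallest of m is the largest of min(1, (m − j + 1) × p(j)) over j = 1, …, i.

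The cost is a sentence in the plan. The same p-values are used, no new data are needed, and the adjustment can be done by hand. Where simultaneous intervals are wanted, Bonferroni-width intervals can still be shown, with a note that they may include 1 for a Holm-significant hazard ratio. If the sponsor intends a single family across papers that appear at different times, keep a fixed 0.05/m, with m stated in advance.
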